7.3 LOST TO FOLLOW-UP

A participant will be considered lost to follow-up if he or she fails to return for 1 scheduled study visit and is unable to be contacted by the study site staff.

The following actions must be taken if a participant fails to return to the clinic for a required study visit:

- The study team will attempt to contact the participant and reschedule the missed visit within 2 weeks and counsel the participant on the importance of maintaining the assigned visit schedule and ascertain if the participant wishes to and/or should continue in the study.
- Before a participant is deemed lost to follow-up, the study team will make every effort to contact with the participant (where possible, 3 telephone calls, emails or text messages). These contact attempts should be documented in the participant's research record.
- Should the participant continue to be unreachable, he or she will be considered to have withdrawn from the study with a primary reason of lost to follow-up.

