12 NOVEMBER 2019

		p		nent	
OnCore Calendar Segment	Pre-Study	Consented OnStudy		OnTreatment	Off Study
Study Timeline	Pre-screening (Pre-consent)	Visit 1 Day 1	Visit 2 Day 168 ±7	Phone Call- Intervention Arm Day 252 ±14	Visit 3 Day 336 ±21
EMR Review Eligibility	х				
Informed Consent		х			
Demographics		х			
Clinical history		х			
Randomization		х			
Provide FitBit and Instruction to Intervention Arm		х	х		
Outcome Evaluation					
Vitals + Anthropometrics: blood pressure, height, weight, waist and hip circumference		х	х		х
Blood Work: ¹ hepatic panel, platelets, A1c, fasting insulin, glucose, lipid panel		х	х		х
6MWT		Х	х		х
Hand Grip Strength		х	х		х
Quality of Life Questionnaire ⁴		х	х		х
Physical Activity Survey (IPAQ) ⁴		х	х		х
Motivation to Change Questionnaire ⁴		х	Х		х
Dietary Survey ⁴		х	Х	х	х
Dietician Assessment ²		х			
VCTE ¹		х	Х		х
MRE1 ^{1,3}		х	Х		
Exit Interviews			Х		х
Adverse Events Reporting		х	Х	Х	х

Table 2. Arm II - wait list control; receives intervention after visit 2

¹Baseline results can be abstracted from medical record if performed within prior 6 months and <5% weight change since that time. Otherwise, VCTE will be performed +/- 14 days from enrollment. Hepatic panel and platelet count are standard of care measures. Remainder of imaging and laboratory data will be research costs. ²Can be done +/- 14 days from enrollment in person or via telephone

³ Only done in half of patients due to cost, determined by computer randomization with stratification according to liver disease stage (cirrhosis)

⁴ If not enough time during enrollment, participants will be sent a link via email to complete the surveys within 14 days from enrollment date.

EMR, electronic medical record; 6MWT, 6 minute walk test; IPAQ, International Physical activity Questionnaire; VCTE, vibration controlled transient elastography; MRE, magnetic resonance elastography

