At our center, patients with NAFLD /NASH without decompensated cirrhosis are seen every 6-12 months. Visits are approximately 15-20 minutes and consist of review of BMI/weight, recent hepatic panel and Fibroscan if ordered. Management typically consists of a breif overview of lifestyle changes including improvements in nutrition and physical actiity. Vitamin E is prescribed In a small proportion of patients. A similarly small proportion of patients are formally referred to and subsequently evaluated by a nutritionist.

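### Section 7.3 can class a participant who misses Visit 2 and stays unreachable as withdrawn about 140 days before Visit 3, with no provision for attending Visit 3 or for retrieving outcomes from the medical record

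*Combined protocol and SAP*

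**What the plan says.** Section 7.3 sets a two-part trigger: "A participant will be considered lost to follow-up if he or she fails to return for 1 scheduled study visit" and, in addition, cannot be reached by site staff. Before the label applies, staff must "attempt to contact the participant and reschedule the missed visit within 2 weeks" and make documented contact attempts ("where possible, 3 telephone calls, emails or text messages"). If these fail, "he or she will be considered to have withdrawn from the study with a primary reason of lost to follow-up".

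The schedule in section 1.3 has two post-baseline visits. Visit 2 is Day 168, ±14 days in Table 1 (Arm 1) and ±7 days in Table 2 (Arm 2). Visit 3 is Day 336 ±21 in both. Section 3 places the primary endpoint at 6 months; section 9.3.2 adds maintenance of the CAP reduction at 12 months.

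On the medical record, footnote 1 to the schedule says that baseline "results can be abstracted from medical record if performed within prior 6 months", subject to a limit on weight change. The footnote is attached to blood work, VCTE and MRE. The weight row does not carry it. Section 8.1 allows historical Fibroscan results under a differently worded weight condition. Under Usual Care, section 6.1.1 describes clinic visits every 6 to 12 months: "Visits are approximately 15-20 minutes and consist of review of BMI/weight, recent hepatic panel and Fibroscan if ordered". Section 10.1.6.1 names the electronic record as a source of clinical data in general.

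**The concern.** Silence after one missed visit is given the same status as a decision to leave. Section 7.2 describes withdrawal as the participant's request or an investigator's decision for listed reasons, and being unreachable is neither. Section 7.1 takes the opposite approach for people who stop the intervention: they stay in the study and their remaining procedures continue. No equivalent sentence covers someone who cannot be reached around Day 168 but might be reachable, or might attend, around Day 336.

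What is at stake is outcome data that could still be obtained. Section 9.3.2 offers only a modified intention-to-treat analysis and a completers' analysis when follow-up imaging is missing, and names no method for the missing values. Each value lost without need therefore bears directly on the CAP results, at 12 months through a closed Visit 3 and at 6 months through clinic results that nobody is told to look for.

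**Working it through.** **1. When the label can apply after a missed Visit 2** (windows from section 1.3, rescheduling period from section 7.3)

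| | Arm 1 | Arm 2 |
|---|---|---|
| Visit 2 window closes | 168 + 14 = Day 182 | 168 + 7 = Day 175 |
| Plus 2 weeks | 182 + 14 = Day 196 | 175 + 14 = Day 189 |
| Days to nominal Visit 3 | 336 − 196 = 140 | 336 − 189 = 147 |

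The Visit 3 window closes at 336 + 21 = Day 357. This counts the 2 weeks from the close of the Visit 2 window, which is one reading of section 7.3. Counting from the nominal visit day would bring the label forward.

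**2. What the record could supply**

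- VCTE/CAP and laboratory results: accepted from the record at baseline (footnote 1, section 8.1), so there is a precedent.
- Weight: measured at Visits 1, 2 and 3, with no baseline provision for abstraction. Section 6.1.1 shows only that clinic weights are reviewed in routine care.
- Conditions: footnote 1 requires less than 5% weight change since the test; section 8.1 requires no weight loss above 5% in the prior 12 months. Either condition, carried over to follow-up, would tend to exclude people who lost weight, which is the response that the trial hopes to see.

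**3. Upper bound on the number affected**

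Section 9.2 anticipates dropout of up to 20%: 0.20 × 120 = 24, or 12 of 60 per arm if equal. This covers every kind of dropout, and the documents do not say how much of it would arise under section 7.3. The planned total of 120 cannot be reproduced, because no effect size, control rate or standard deviation is given; the present point does not depend on it.

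**4. How much missing outcomes could matter, at that bound**

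With a fraction m missing in each arm, the best-case to worst-case range for the difference in response rates has width m + m. The recovered shares below are assumptions; the documents give none.

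| Missing outcomes recovered | Still missing per arm | Width of range |
|---|---|---|
| 0% | 12/60 = 20% | 40 points |
| 25% | 9/60 = 15% | 30 points |
| 50% | 6/60 = 10% | 20 points |

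This is an illustration of scale, not a forecast of what record retrieval would achieve.

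**The case against.** The strongest reply is that section 7.3 is less severe than it may look. The label is not automatic: it needs a missed visit, an attempt to rebook and failed, documented contact. Anyone who is reached is not lost. All of that stands, and what remains is the absence of any provision once contact has failed.

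A reader might infer that section 7.3 ends data collection or discards clinic values. The text says neither. It does not bar someone who resurfaces from Visit 3, and section 10.1.6.1 permits data entry from the electronic record without limiting it to baseline. Nor is it evidence that record review appears in the schedule only at pre-screening: that row concerns eligibility, and baseline abstraction is not marked there either. The supportable statement is that the plan makes no provision, and that the word withdrawn points staff towards stopping.

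A reader might also infer that loss will differ by arm, because Arm 1 has regular feedback and a Day 84 call, whereas Table 2 shows no study contact for controls between the baseline procedures and Visit 2. Against this, controls begin the intervention after Visit 2, and both arms are paid $25 per visit. The documents support neither a direction nor a size.

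The doubts about yield stand. Fibroscan is done only if ordered, clinic visits are 6 to 12 months apart, some recruits come from other local clinics (section 1.1), and people who miss study visits may also miss clinic visits.

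**Conclusion.** The point holds as a gap with a practical consequence. One missed visit followed by silence leads to withdrawn status up to about 140 to 147 days before a visit whose CAP value the analysis section uses, and the protocol neither keeps that visit open nor directs staff to the record. This is out of step with its own approach to people who stop the intervention.

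The size cannot be determined from the documents. It would be wrong to say that section 7.3 costs 24 participants their outcome: that figure is the ceiling for all dropout, including people who ask to leave. It would also be wrong to cite weight as already accepted from the record at baseline, or to expect a Visit 3 invitation to rescue the 6-month endpoint. The conclusion rests on reading withdrawn in its ordinary sense; if the investigators intend such participants to remain eligible for Visit 3, the protocol should say so.

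**What to change.** **Status definitions.** In section 7.3, define missed visit, lost to follow-up and withdrew consent separately. Anyone who missed Visit 2 and has not withdrawn consent stays eligible for Visit 3 and is invited to it. Class that person as lost only when the window closes on Day 357 without contact.

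**Labelling.** An Arm 2 participant who missed Visit 2 may not have started the intervention. Record whether it was started, and do not treat the Visit 3 value as post-intervention by default.

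**Record retrieval.** Where consent allows, abstract the record CAP/VCTE, laboratory values and clinic weight nearest Day 168 for participants without Visit 2 data. Use one pre-set window for both arms, and do not apply the baseline weight-change conditions. Flag the values as record-sourced and use them only in a sensitivity analysis, reported beside the analysis without them.

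**Cost.** About a paragraph in section 7.3, a sentence in section 9.3.2 and some chart abstraction. The consent wording on record access should be checked; if it does not cover this use, enrolled participants may need to consent again. Record values are unscheduled and selectively obtained. An equal window does not make test ordering equal between arms, which is why they belong in a sensitivity analysis.

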8 STUDY ASSESSMENTS AND PROCEDURES

8.1 ENDPOINT AND OTHER NON-SAFETY ASSESSMENTS

-Baseline & Outcome Assessments

1) Demographics and Medical History: alcohol use, components of metabolic syndrome, diabetes, thyroid disease, depression, cirrhosis, NAFLD vs NASH.

2) Physiologic Measures: blood pressure, weight, BMI, waist circumference, waist to hip ratio

3) Physical Function and Frailty Measures: 6 Minute Walk Test (6MWT) to assess baseline physical function (validated among patients with chronic liver disease)(13) and hand grip strength;(14)

4) HRQOL and Stages of Change: CLDQ-NAFLD for HRQOL and the validated motivation to change behavior questionnare.(16)

5) Laboratory studies: hepatic panel, platelet count, lipid panel, glucose and hemoglobin A1c (abstracted if obtained within the last 6 months; otherwise ordered at time of clinic visit). If laboratory studies are ordered for study purposes, blood for hepatic panel, lipid panel and glucose will be obtianed in 1 serum separator tube (SST) (3mL). One lavender tube will be used to collect specimen for platelet count (3mL), and another 1 lavender tube will be used for hemoglobin A1c. The total amount of blood drawn from patients will not exceed 20 mL, and will be kept within the IRB restrictions.

6) Hepatic Imaging: all patients will complete a fibroscan to assess liver stiffness and CAP measurements unless performed within prior 6 months. Historical results for prior testing will only be used if patients had not had >5% weight loss in prior 12 months. Due to cost limitations, a total 50 patients will have MRE with

PDFF. MRE exams will be evenly assigned by computer randomization with stratification according to liver stage (cirrhosis, no cirrhosis) and subcategory (NAFLD vs NASH) in each arm.

Phone Call: Patients receiving the intervention will receive a phone call to review baseline data results after 3 months of intervention. They will also complete a second nutritional questionnaire. Patients will also be given detailed feedback and recommendations on step counts and nutrition thus far.

8.2 SAFETY ASSESSMENTS

In order to screen for potential study participants, our clinical research staff with review the electronic health record (EHR) in compliance with HIPPAA protocol.

Individuals enrolled in the study will complete the following procedures/evaluations to monitor clinical status and occurrence of adverse events:

- **Physical examination:** weight, waist and hip circumference.
- Vital signs: blood pressure
- Radiographic or other imaging assessments: VCTE and MRE
- **Biological specimen collection and laboratory evaluations**: Platelet count, hepatic panel, lipid panel (fasting), hemoglobin A1c, fasting insulin
- Assessment of adverse events: to be assessed at 3-month phone call, 6 and month follow-up visits. Patients will also be asked to self-report AEs of interest (with focus on falls and other activity-related musculoskeletal injuries) during weekly eHealth communications.

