While highly regimented lifestyle programs have shown to be efficacious, they are often costly, not accessible to many patients, and not amenable to long term sustainability and scalability.(7) Data from the obesity literature indicates that programs that remove logistical barriers (time constraints, cost) and increase the frequency of interactions/ follow-up with real-time feedback have a higher likelihood for real world effectiveness. Mobile technology based lifestyle programs encompass many of these features and have proven to be effective for weight loss among cohorts with similar phenotypes.(8) Preliminary data from our initial pilot trial of a mobile technology-based lifestyle program among NAFLD patients suggest feasibility and efficacy in terms of positive impact on weight loss, physical function, HRQOL and liver and metabolic parameters. Data from a small cohort of NAFLD patients also demonstrated a mobile technology program (text messaging) was effective in promoting weight loss (mean decrease 11-lb compared to none in control group).(9)

In order to assess outcomes of interest, we will employ validated non-invasive biomarkers to assess changes in hepatic steatosis and fibrosis. This includes VCTE, an ultrasound based test that can capture both amount of steatosis via controlled attenuation parameter (CAP) and fibrosis via liver stiffness

measurements. More recently, MRI based imaging tests, MR elastography (MRE) has been shown to have excellent accuracy for assessment of both fibrosis (elastography) and hepatic steatosis (via proton density fat fraction – PDFF). (10) Lifestyle interventions in the general obesity literature and among NAFLD cohorts have been shown to have excellent safety profile with no to minimal adverse events, with primary concern being falls or other musculoskeletal related injuries.

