2.3 RISK/BENEFIT ASSESSMENT

2.3.1 KNOWN POTENTIAL RISKS

The risks related to dietary changes and increase in physical activity are minimal, with overall systemic benefit improvements likely far outweighing any potential risks. So long as dietary restriction does not involve > 30% reduction in total caloric intake per day, risks to calorie restriction should be minimal. (11) Regarding physical activity, the overwhelming majority of individuals will be able to partake in a walking program with minimal to no risk. More vigorous exercise will be implemented based on baseline fitness and other factors that may impact potential to achieve higher METS. Potential, but unlikely risks include falls or other musculoskeletal injuries resulting from physical activity, or cardiac events among individuals with cardiac disease who engage in overly ambitious exercise regimens in an unsupervised setting. In terms of survey instruments, these risks are also minimal and rare, but include the potential for feelings of discomfort or anxiety related to answering personal questions. Participants will be able to opt out of answering questions that are discomforting to them. For participants completing MREs, there is a risk of feeling anxious or claustrophobic, transient changes in hearing due to clanging of the machine (rare), and risk related to indwelling metal that can be impacted by the machinery, but this will be addressed with proper screening. Lastly there is a risk of breach of confidentiality and privacy associated with being in the study, including potential breach of the FitBit app.

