6 STUDY INTERVENTION(S) OR EXPERIMENTAL MANIPULATION(S)

6.1 STUDY INTERVENTION(S)

6.1.1 STUDY INTERVENTION OR EXPERIMENTAL MANIPULATION DESCRIPTION

This is a randomized trial comparing a structured mobile technology-based lifestyle intervention compared to usual care.

Intervention

-Education: Patients in the intervention arm will receive our NAFLD educational folder with an overview of contents by study staff. The folder includes: 1) NAFLD disease information including diagnosis, clinical manifestations, natural history and treatments; 2) NAFLD nutritional recommendations including sample menus; 3) NAFLD physical activity recommendations including walking programs and physical activity logs; 4) weight tracking logs; and 5) resources for diet and exercise programs.

-**Physical Activity**: All participants in the intervention arm (N=60) will receive a FitBit Zip for monitoring of step counts. The Fitbit wirelessly syncs data from the tracker to the Fitbit software or app. Study staff will assist with downloading the software and will instruct participants to wear their FitBit during waking hours every day. At any time if the participant has questions or problems regarding the use of the FitBit, a study staff member can be contacted. Study staff will retrieve users' step count data for analysis weekly and will provide subject with personalized feedback on physical activity with tailored step count goals (10% increase per week with max increase 800 steps per week to a maximum of 10,000 steps/week) and motivational messaging via e-mail. Patients with consecutive days without data recorded or with other signs of low FitBit usage (days with minimal step counts) will be contacted by study staff via e-mail or phone if necessary to encourage use. Feedback will occur weekly for the first 3 months of the intervention and then transition to biweekly for the last 3 months. Participants will also complete the short-version IPAQ for physical activity at enrollment, 6 month and 12 month follow-up visits.

-Nutrition: Patients in the intervention arm will have a nutritional assessment by a GI nutritionist specializing in NAFLD either at the enrollment visit if time allows, or in a separate in person or phone assessment within the first 2 weeks of enrollment. All patients will also complete the "Starting the Conversation" nutritional questionnaire for patients with metabolic disease at enrollment, 6 month and 12 month follow-up visits.(15)

Usual Care

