8.3.4 TIME PERIOD AND FREQUENCY FOR EVENT ASSESSMENT AND FOLLOW-UP

The occurrence of an AE or SAE may come to the attention of the study team during study visits and routine study participant contact throughout their participation in the study.

All AEs including (including SAEs) will be captured on the appropriate CRF. Information to be collected includes event description, date of onset, PI's assessment of severity, relationship to study intervention, and time of resolution/stabilization of the event. All AEs occurring while on study must be documented appropriately regardless of relationship. All AEs will be followed to adequate resolution.

Any medical condition that is present at the time that the participant is screened will be considered as baseline and not reported as an AE. However, if the study participant's condition related to their NAFLD/NASH deteriorates at any time during the study, it will be recorded as an AE. Changes in condition in unrelated medical issues with be documented but not reported.

each study visit, the investigator will inquire about the occurrence of AE/SAEs since the last visit. Events will be followed for outcome information until resolution or stabilization.

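### The recurring self-report prompt for adverse events focuses on falls and musculoskeletal injury but not on cardiac events, the other exercise risk the protocol names, and its weekly frequency does not match section 6.1.1

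*Combined protocol and SAP*

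**What the plan says.** Section 2.3.1 (Known Potential Risks) lists the harms that physical activity could cause. Beside falls and musculoskeletal injury it names "cardiac events among individuals with cardiac disease who engage in overly ambitious exercise regimens in an unsupervised setting". It describes all of these as potential but unlikely.

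Section 8.2 (Safety Assessments) sets up two routes for finding adverse events. The first is general enquiry, "to be assessed at 3-month phone call, 6 and month follow-up visits" (a month is missing from that line as we have it; the Schedule of Activities in 1.3 shows adverse-event reporting at both Visit 2 and Visit 3). The second is a recurring prompt, in which participants are asked to "self-report AEs of interest (with focus on falls and other activity-related musculoskeletal injuries) during weekly eHealth communications".

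Section 8.3.4 adds that at each study visit "the investigator will inquire about the occurrence of AE/SAEs since the last visit", and that "All AEs occurring while on study must be documented appropriately regardless of relationship".

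On how often participants are contacted, section 6.1.1 says: "Feedback will occur weekly for the first 3 months of the intervention and then transition to biweekly for the last 3 months".

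**The concern.** The recurring prompt is the part of the safety plan that operates while step goals are being raised and nobody is supervising the exercise. It is aimed at one of the harms named in 2.3.1 and does not name the other. A participant who has chest discomfort or palpitations in week 3 and does not volunteer it is next asked about adverse events in general at about week 12.

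Two things are at stake. One is how soon the team hears of a non-serious cardiac symptom. The other is how the safety summary promised in 9.3.4 can be read. If one kind of event is asked for by name many times and the other only in general terms at a few contacts, a low cardiac count is hard to tell from a low rate of asking.

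Separately, staff cannot tell from 8.2 and 6.1.1 together how often the prompt is to be sent in the second half of the intervention.

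**Working it through.** The plan gives no figure to reproduce here. The check compares the sections and counts the contacts.

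**Inputs**
- Intervention period, Arm 1: Day 1 to Day 168, with the phone call at Day 84 (1.3, Table 1).
- Intervention period, wait-list arm: Day 168 to Day 336, with the call at Day 252 (1.3, Table 2).
- Stated prompt frequency: weekly (8.2).
- Feedback frequency: weekly for 3 months, then biweekly for 3 months (6.1.1).

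**Step 1: content of the prompt against the named risks**

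| Activity-related risk in 2.3.1 | Named in the recurring prompt (8.2) | Covered by general enquiry (8.2, 8.3.4) |
|---|---|---|
| Falls, musculoskeletal injury | Yes | Yes |
| Cardiac events in people with cardiac disease | No | Yes |

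**Step 2: spacing of the general enquiries**
- Arm 1: 84 / 7 = 12 weeks to the call, then (168 − 84) / 7 = 12 weeks to Visit 2.
- Wait-list arm: (252 − 168) / 7 = 12 weeks, then (336 − 252) / 7 = 12 weeks.

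These are nominal intervals; the visit windows can shorten or lengthen them.

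**Step 3: number of prompts in one intervention period**
- Length: 168 / 7 = 24 weeks, or 12 weeks in each half.
- Weekly throughout, as 8.2 reads: 12 + 12 = 24.
- On the 6.1.1 timetable, with biweekly read as every two weeks: 12 + 12/2 = 12 + 6 = 18.
- With biweekly read as twice a week: 12 + 12 × 2 = 36. This is the less natural reading, because the text describes a transition from weekly contact.

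On either reading of biweekly, weekly is not the frequency in months 4 to 6. The counts of 18 and 36 assume that the eHealth communications of 8.2 are the feedback messages of 6.1.1. The documents do not say so, but they describe no other recurring contact with participants.

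**Step 4: ascertainment of the two risks side by side**

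During one intervention period after its starting visit, falls and musculoskeletal injury receive about 18 targeted prompts (24 if weekly throughout) plus 2 general enquiries. Cardiac events receive no targeted prompts and the same 2 general enquiries.

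**The case against.** The best defence is that a focus is not an exclusion. Section 8.2 gives no closed list, and nothing stops a participant from reporting a cardiac symptom in reply to any message. The Day 84 call is itself an adverse-event enquiry between visits. Section 8.3.4 requires open enquiry at each visit, recognises that events may surface in routine contact, and requires documentation whatever the cause. A cardiac event that led to hospital admission would be a serious adverse event under 8.3.2 and is unlikely to be forgotten by the next visit. All of this stands. A reader might infer that cardiac events would go unrecorded in this trial; the documents do not support that.

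The focus also has a stated reason. Section 2.2 gives the "primary concern being falls or other musculoskeletal related injuries", and minor falls and strains are plausibly what people forget over 12 weeks. Section 5.2 excludes cardiovascular events in the last 3 months. This explains why falls and injuries are prompted for; it does not explain why the other named risk is not. The exclusion is headed by recent events, so older or stable cardiac disease is not clearly excluded, and people with cardiac disease are the group that 2.3.1 identifies.

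On frequency, a reader might infer that prompting stops after month 3. It does not: on the natural reading it continues every two weeks. Section 6.1.1 also speaks of feedback and 8.2 of communications, so the two could differ, in which case the protocol should say so.

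**Conclusion.** The point holds as a modest gap in targeted prompting, together with a wording conflict on frequency. The recurring prompt names one of the two kinds of activity-related harm in 2.3.1. For the other, participants rely on volunteering a report or on general enquiries about 12 weeks apart. The practical effect falls mainly on non-serious cardiac symptoms, and ascertainment of the two risks is uneven: about 18 to 24 targeted prompts against none.

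The frequency conflict amounts to 18 prompts rather than 24, all of the difference falling in months 4 to 6. That figure rests on two assumptions: that the contacts in 8.2 and 6.1.1 are the same, and that biweekly means every two weeks.

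A reader might go further and conclude that the reported safety profile will be distorted by a known amount, or that serious cardiac events will be missed. The documents give no event rates from which to estimate the first, and their general adverse-event rules argue against the second. No primary or secondary efficacy analysis depends on this point. It is a cheap improvement to safety ascertainment.

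**What to change.** In 8.2, add cardiac symptoms and events to the adverse events of interest asked for in the existing eHealth communications, so that the list matches 2.3.1.

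Reconcile the word weekly in 8.2 with 6.1.1 in one of two ways: keep a short adverse-event question weekly through month 6 even when step feedback is less frequent, or state the actual frequency in 8.2. Either way, say whether the communications in 8.2 are the feedback messages in 6.1.1.

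The cost is one added item in a message already being sent and, if the question stays weekly, about 24 − 18 = 6 more short messages per participant. The downside is a few more minor reports to review. The change concerns only what is asked and how often; how a positive reply is managed stays with the investigator.

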1.3 SCHEDULE OF ACTIVITIES

Table 1 - Arm 1 - active intervention w/follow up

OnCore Calendar Segment	Pre-study	Consented OnStudy OnArm/OnTreatm	On treatment	On FollowUp	OffStudy
Study Timeline	Pre-screening (Pre-consent)	Visit 1 Day 1	Phone Call- Intervention Arm Day 84 ±7	Visit 2 Day 168 ±14	Visit 3 Day 336 ±21
EMR Review Eligibility	х				
Informed Consent		Х			
Demographics		Х			
Clinical history		Х			
Randomization		Х			
Provide FitBit and Instruction to Intervention Arm		х		х	
Outcome Evaluation					
Vitals + Anthropometrics: blood pressure, height, weight, waist and hip circumference		х		х	х
Blood Work: ¹ hepatic panel, platelets, A1c, fasting insulin, glucose, lipid panel		х		х	х
6MWT		х		х	х
Hand Grip Strength		х		х	х
Quality of Life Questionnaire		Х		х	х
Physical Activity Survey (IPAQ)		х		х	х
Motivation to Change Questionnaire		Х		х	х
Dietary Survey		Х	Х	х	х
Dietician Assessment ²		Х			
VCTE ¹		Х		х	х
MRE1 ^{1,3}		Х		Х	
Exit Interviews				Х	х
Adverse Events Reporting		x	Х	х	х

Version <3.0>

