9.3.4 SAFETY ANALYSES

A summary statistic of any adverse events will be provided.

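### Up to Day 168 the intervention arm is asked about adverse events more often than controls, so an adverse-event summary by arm could show an excess produced by ascertainment

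*Combined protocol and SAP*

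**What the plan says.** Section 8.2 has AEs assessed at the 3-month call and the follow-up visits, and adds that patients will report AEs of interest themselves, chiefly falls and musculoskeletal injuries, "during weekly eHealth communications". The sentence names no arm.

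Section 8.1 limits the call: "Patients receiving the intervention will receive a phone call to review baseline data results after 3 months of intervention". In Section 1.3, Table 1 heads the column "Phone Call- Intervention Arm Day 84 ±7" and marks AE reporting there, as well as at Visits 1, 2 and 3. In Table 2 (wait list) the row "Adverse Events Reporting" is marked at Visit 1, Visit 2 (Day 168), a call on Day 252 and Visit 3.

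Regular electronic contact appears in Section 6.1.1 only under the intervention: step-count goals and "motivational messaging via e-mail". Its frequency is given as: "Feedback will occur weekly for the first 3 months of the intervention and then transition to biweekly for the last 3 months". The usual-care description mentions clinic visits and no messaging.

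Section 8.3.4 has the investigator ask at each study visit, in both arms, about events since the previous one. Section 9.3.4 is a single sentence: "A summary statistic of any adverse events will be provided". It gives no arm, period, denominator or source of report.

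**The concern.** How many AEs are reported depends on how often, and how soon after the event, people are asked. Here the asking is tied to the treatment. Someone on the intervention who trips while walking in week 5 can mention it in a message that week or at the Day 84 call. A control with the same fall is first asked at Visit 2, months later.

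The extra prompts aim at the very harm that Section 2.2 names as the main safety worry for lifestyle programmes. Minor falls and strains are also plausibly the events most easily forgotten. The trial is unblinded (Section 6.3), so nothing else in the design offsets the difference. If AEs to month 6 are set out by arm, as readers of a randomised trial would expect, an excess on the intervention could not be told apart from the effect of more frequent asking.

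**Working it through.** The plan gives no AE rate and no AE comparison, so it has no figure of its own to reproduce. The check has two steps.

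**Step 1: scheduled AE enquiries after baseline, to Day 168** (168 / 7 = 24 weeks). Visit 1 on Day 1 is left out for both arms, because it is baseline.

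| Reading | Intervention | Control |
|---|---|---|
| Section 1.3 tables only | call + Visit 2 = 1 + 1 = 2 | Visit 2 = 1 |
| Prompts follow the 6.1.1 feedback schedule | 12 weekly + 6 biweekly (every two weeks) + 1 + 1 = 20 | 1 |
| Prompts weekly throughout, as 8.2 reads | 24 + 1 + 1 = 26 | 1 |

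The wait-list call comes 252 − 168 = 84 days after Visit 2, so it adds nothing to the randomised comparison. On the tables alone, the longest gap between AE enquiries is 168 − 84 = 84 days in the intervention arm and 168 − 1 = 167 days in controls.

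The second and third rows differ because 8.2 calls the communications weekly, while 6.1.1 makes the feedback biweekly after 3 months. The two sections need reconciling.

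**Step 2: what unequal capture does when true risk is equal.** Expected participants with a reported AE = N × p × c, where
- N = 60 per arm (Section 4.1);
- p = true 6-month risk, assumed 20% in both arms;
- c = probability that an affected participant's AE is reported, assumed.

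The ratio is (N × p × c_I) / (N × p × c_C) = c_I / c_C, so it does not depend on N or p.

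| c_I, c_C | Intervention | Control | Ratio |
|---|---|---|---|
| 0.95, 0.80 | 60 × 0.20 × 0.95 = 11.4 | 60 × 0.20 × 0.80 = 9.6 | 1.19 |
| 0.90, 0.60 | 60 × 0.20 × 0.90 = 10.8 | 60 × 0.20 × 0.60 = 7.2 | 1.50 |
| 0.90, 0.40 | 10.8 | 60 × 0.20 × 0.40 = 4.8 | 2.25 |
| 0.90, 0.90 | 10.8 | 10.8 | 1.00 |

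No capture value comes from the documents. The direction follows whenever capture is lower in controls; the size cannot be fixed.

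**The case against.** - **Section 9.3.4 promises no comparison.** A reader might infer that the plan merges all sources into one table by arm, and that this table will show an excess. The documents say neither. Section 9.3.4 mentions no pooling, arm or test, and Section 9.1 has no safety hypothesis. This stands, so the point is conditional: a summary by arm can be distorted.
- **Both arms are asked at Visit 2 about the whole interval (Section 8.3.4).** This stands, and the remedy builds on it. It does not settle the matter. Section 9.3.4 does not rest on that enquiry, the AE items listed in 8.3.4 do not include how the event came to light, and 8.3.4 also accepts events learned in routine contact, which is more frequent on the intervention.
- **The prompts are not expressly limited to one arm.** The sentence in 8.2 refers to patients generally, and Table 2 marks the FitBit row at Visit 1 for the wait list too. The restriction is an inference from 6.1.1, though a sound one. If controls received the same prompts, the imbalance would shrink to the Day 84 call.
- **The size is unknown.** A reader might infer an apparent ratio of 1.4 to 3.3 by supposing that controls report 30% to 70% of events (1/0.7 = 1.43; 1/0.3 = 3.33). That also takes intervention-arm capture as complete, and the documents support neither assumption. Nor would it apply to all AEs: the prompts focus on falls and injuries, and recall loss that large is least plausible for serious events.
- **The stakes are small.** This is a pilot, Section 2.3 describes the risks as minimal, and AEs are not an endpoint. The bias would overstate harm from the intervention, not hide it. All of this stands and keeps the point minor.

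**Conclusion.** The point holds as a minor one. The documents state outright that controls have no counterpart to the Day 84 call before Day 168. That the message prompts go only to the intervention arm is inferred from 6.1.1. The imbalance is 2, 20 or 26 enquiries against 1, depending on the reading.

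Reported AEs to month 6 can therefore be higher in the intervention arm at equal true rates, mainly for minor falls and musculoskeletal injuries. The ratios of 1.19 to 2.25 illustrate assumed capture and are not estimates. It would go too far to say that the planned summary will differ by arm through ascertainment alone: the plan does not commit to a summary by arm, and recall at Visit 2 is unknown.

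**What to change.** - **CRF:** add one field for the source of each AE (visit, call, message or e-mail). Without it, the routes cannot be separated later.
- **Section 9.3.4:** state arm, period and denominators. Base the summary by arm for months 0 to 6 on the Visit 2 enquiry, put to both arms for the whole interval from Day 1. Count an event mentioned there even if it was already reported by message or call. List events known only from messages or the call separately, as intervention-arm data.
- **Section 8.2:** say which arm receives the prompts, and reconcile their frequency with 6.1.1. Send controls the same AE question by e-mail at month 3, to match the Day 84 call; list separately any event known only from that e-mail.

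The cost is one CRF field, one table and one short e-mail to 60 controls. The e-mail would be new: the survey link in footnote 4 to the schedule tables serves only questionnaires left unfinished at enrolment, within 14 days.

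This reduces the imbalance but does not remove it. Controls would have 2 enquiries against 2, 20 or 26, and repeated prompting may still improve intervention-arm recall at Visit 2. The report should say so.
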